### ***All Other Variables***

**Demographics.** Immediately pre-intervention, participants will be asked to report on the following demographic variables: age, sex assigned at birth, gender identity, race/ethnicity, sexual/romantic attraction and orientation, mental health treatment history, and zip code.

**Perceived Socioeconomic and Social Status.** Immediately pre-intervention, participants will be asked to rate their perceived socioeconomic and social status using the two items from the MacArthur Scale of Subjective Social Status-Youth Version (Goodman et al., 2001). Respondents indicate where they see themselves on a ladder with 10 rungs (range: 1 to 10 for both items, where 1 = families with most money/education/jobs and youth with highest respect/grades/social standing; 10 = families with least money/education/jobs and youth with lowest respect/grades/social standing).

<https://doi.org/10.1542/peds.108.2.e31>

**Pubertal Development.** Pubertal development will be measured pre-intervention via the the Pubertal Development Scale (Carskadon & Acebo, 1993). This scale asks participants to rate 5 items relating to their physical development milestones (e.g. "body hair growth") on a 5-point Likert scale (1 = "not yet started"; 2 = "barely started"; 3 = "definitely started"; 4 = "seems complete"; 5 = "I don't know/Not applicable"). Excluding "5" responses, higher scores generally indicate being further along in pubertal development.

[https://www.jahonline.org/article/1054-139X\(93\)90004-9/pdf](https://www.jahonline.org/article/1054-139X(93)90004-9/pdf)

**Discrimination.** The Expanded Everyday Discrimination Scale will be measured pre-intervention to gauge the levels of relatively minor, every-day, chronic discrimination experienced by participants. The original scale (Williams et al., 1997) asks participants, "In your day-to-day life, how often do any of the following things happen to you?" for 9 items (e.g. "you are treated with less courtesy than other people are") on a 5-point Likert scale (1= "never"; 6 = "almost every day"). These items assess the participant's observations about how others treat and act around them on a daily basis. The expanded version of this scale includes a 10th item, "You are followed around in stores." Scores on the Expanded Everyday Discrimination Scale range from 10-60, with higher scores indicating higher levels of chronic discrimination experienced by participants. Respondents are also asked to identify what they believe to be the main reason(s) for these experiences (e.g. gender, race, age, etc.).

[https://scholar.harvard.edu/files/davidrwilliams/files/measuring\\_discrimination\\_resource\\_june\\_2016.pdf](https://scholar.harvard.edu/files/davidrwilliams/files/measuring_discrimination_resource_june_2016.pdf)

**Self Hate.** Self-hate will be assessed immediately pre-intervention, post-intervention, and follow-up using the Self Hate Scale (Turnell, Fassnacht, Batterham, Calear, & Kyrios, 2019), which is measured on a 7- point Likert scale. The Self Hate Scale asks participants to "Rate how true each of the following statements are for you right now, in this moment" for 7 items (e.g. "I hate myself"; 1 = "not at all true for me"; 7 = "very true for me"). Scores on the Self Hate Scale range from 7-49, with higher scores indicating higher levels of self hate.

<https://www.sciencedirect.com/science/article/abs/pii/S0165032718313144>

**Disordered Eating.** Disordered eating behaviors will be measured at pre-intervention and 3-month follow-up using The Dietary Restriction Screener (DRS-2; Haynos & Fruzzetti, 2015). The DRS-2 is a 9-item measure evaluating restrictive eating, bingeing, and purging behaviors in participants. 6 items ask participants whether or not they have engaged in restrictive eating, bingeing, or purging behaviors in the past year or in the past 3 months (0 = no; 1 = yes). The other 3 items assess the frequency of these behaviors over the past 28 days.

<https://link.springer.com/article/10.1007/s40519-014-0161-0>

**SSI Feedback.** Acceptability and participant perception of each SSI will be assessed using the Program Feedback Scale (PFS). This scale was adapted for web-based SSIs (Schleider, Mularkey, & Weisz, 2019) and is based on validated acceptability measures used for digital interventions. The PFS asks participants to “Please tell us how much you agree with each statement below” for 7 statements (e.g. “the activity was easy to use”) using a 5-point Likert scale (1 = “really disagree”; 5= “really agree”). For these 7 items, scores can range from 7 to 35, with higher scores indicating greater acceptability of the SSI (how much participants enjoyed/ understood/ would recommend/ could easily use the SSI). The PFS also assesses qualitative participant feedback with 3 open-ended questions (“What did you like about the program?”, “What would you change about the program?”, and “Is there anything else you’d like to share with us about the program?”). In keeping with other web-based intervention research among youth, we will define a mean score of 3.5 or higher on the PFS (across all 7 items, 1-5 scale) as “acceptable”. We will also report means and standard deviations for each individual item of the PFS (see <https://psyarxiv.com/tdrpc/>).

<https://www.researchprotocols.org/2019/7/e13368/#box1>

#### **How many and which conditions will participants be assigned to? (optional)**

Participants will be randomly assigned to 1 of 2 possible conditions, per a 1:1 allocation ratio: (1) an online, active control group program encouraging feelings disclosure (i.e. supportive therapy SSI), or (2) an online program targeting behaviors and thoughts relating to self-injury (i.e. Project “SAVE”—Stop Adolescent Violence Everywhere—SSI). Random assignment to condition will be conducted in a triple-masked manner. Therefore, participants will be masked to whether they received active treatment and investigators will be masked to which condition the participant is randomized to—as the randomization occurs automatically within the survey. Additionally, as the primary and secondary outcomes are self-report measures, we will not be utilizing an outcomes assessor (e.g. a clinical interviewer). Participants will be informed of their condition assignment following their completion of the full study protocol by debriefing form. Investigators will be informed of participant condition after data collection is complete (i.e. the data analysis phase).

**Supportive Therapy (“Share Your Feelings”) SSI** (Schleider & Weisz, 2019; see <https://osf.io/u4axs/>) is a ~30-minute, self-administered, web-based program that uses components of supportive therapy to encourage feelings sharing. Like Project SAVE, this SSI takes approximately 30 minutes to complete and is self-administered online. The supportive therapy SSI encourages participants in the control group to identify and express their feelings by (1) explaining why sharing feelings is natural, important, and helpful and (2) including testimonials from teens who have shared their feelings with close others.

**Project SAVE (“Stop Adolescent Violence Everywhere”) SSI** is a ~30-minute, self-administered, web-based program that uses components of cognitive behavior therapy and dialectical behavior therapy designed to decrease self-injurious behaviors in youth. The SSI’s content is designed to maximize relevance for youth engaging in self-injurious behaviors by

directly addressing two commonly reported functions of self-injury in youth: using self-injury for self-punishment and/or for emotion regulation. The Project SAVE SSI has 4 general content sections: (1) explaining the science behind how changing your *actions* (i.e. decreasing self-injurious behaviors) can positively impact your *thoughts* and *emotions* over time; (2) providing scientific evidence and testimonials from other teens that have successfully decreased their self-injurious behaviors and noticed positive change as a result; (3) evidence-based tips for overcoming common obstacles to decreasing self-injurious behaviors in day to day life; and (4) offering an opportunity for youth to share their own thoughts and advice on what they have learned with other teenagers who are facing similar challenges. These content areas are reinforced by intervention design features intended to maximize persuasiveness and memorability, in line with other efficacious, web-based SSIs for adolescents.

**Specify exactly which analyses you will conduct to examine the main question/hypothesis. (optional)**

***Testing for Differential Dropout***

First, we will test for differential dropout by study condition. To do this, we will use Z-tests of differential proportions where we compare the proportion of people who drop out before completing the study (Y or N) as a function of treatment condition (0 = control group SSI, 1 = Project SAVE SSI). We will run two tests evaluating differential dropout: (1) measuring dropout prior to finishing our post-intervention questions, and (2) measuring dropout prior to finishing our 3-month follow-up questions. To be considered a study “completer” for the post-intervention questions, a participant must have made it through all post-intervention survey sections (i.e. all sections but “final block” section that presents information for study logistics). To be considered a study “completer” for the 3-month follow-up questions, a participant must have made it through all follow-up survey sections (i.e. all sections but “final block” section that presents information for study logistics).

If the *p* value is greater than .05 we will assume dropout was not dependent on condition assignment and can proceed with interpreting the effects of intervention assignment (i.e. proceed with the between-group analyses exactly as described below, starting in the section labeled “Hypothesis 1”).

If the *p* value for this test is less than .05 we will conclude that dropout was dependent on condition assignment, and we will take the following steps to improve the interpretability of our results. Unequal dropout between treatment groups can introduce bias in trial results; however, this is not always the case (Bell, Kenward, Fairclough, & Horton, 2013; <https://doi.org/10.1136/bmj.e8668>). One major concern is that, if data are *not missing at random*, systematic differences may exist between “dropouts” and “completers” that cannot be corrected for, limiting the interpretability of our results. For example, if more control condition participants experienced a worsening of clinical symptoms and dropped out before completing follow-up measures, this worsening of symptoms would not be captured by completers’ data (or by data imputed based on the available completers’ data). Thus, should unequal dropout exist

between conditions in the present study, we will report the results of our main analyses below, highlighting (1) limitations to interpretation, and (2) ways in which this will inform future intervention development.

Further, if unequal dropout is present, we will run a sensitivity analysis to determine a range of possible effect sizes for our outcomes of interest, varying how much “dropout participants” may have changed on each outcome. To establish lower- and upper-end estimates of effect size, we will: (1) calculate residual change for each of our 3 outcomes, (2) identify the 25th and 75th percentile values for residual change in each outcome, (3) run analyses for each outcome where we impute the lower residual change value (25th percentile) for all dropouts/missing data, as well as the higher residual change value (75th percentile) for all dropouts/missing data. This approach explicitly assumes data are not missing at random, providing a more unbiased estimate of the overall treatment effect in the presence of unequal dropout.

***Testing Hypothesis 1: Do teenagers in the Project SAVE SSI condition report lower self-reported likelihood of future NSSI immediately post-intervention—relative to teenagers in the active control program?***

We will first test if the assumptions necessary to interpret a multiple linear regression are met. If not, we will follow the procedures below. We will document any of these changes when we report our results.

- If assumptions for interpreting a multiple linear regression *are not* met, we will perform a two-way ordinal regression (as this outcome will be Likert data), with pre-intervention likelihood of future NSSI and treatment condition entered as our independent variables, and post-intervention likelihood of future NSSI as the dependent variable. We will consider a p value of less than .05 for treatment condition (in favor of the Project SAVE SSI) as a significant effect of the Project SAVE treatment on likelihood of future NSSI.
- If the assumptions for interpreting a multiple linear regression *are* met, we will enter pre-intervention likelihood of future NSSI as a covariate and treatment condition as the predictor of post-intervention likelihood of future NSSI in a multiple linear regression. We will consider a p value of less than .05 for the treatment condition coefficient (in favor of the Project SAVE SSI) as a significant effect of the Project SAVE treatment on likelihood of future NSSI.

***Testing Hypothesis 2: Do teenagers in the Project SAVE SSI condition endorse lower frequency of SI in the past 3 months—relative to teenagers in the active control program?***

First, we create our secondary outcome variable (i.e. frequency of SI in the past 3 months) by imputing values equal to 0 for participants who endorsed zero SI in the previous 3 months in an earlier question. See “SI Frequency in the Past 3 Months” under the key dependent variables section for more details.

Next, we will determine whether a Poisson regression, a negative binomial regression, a zero-inflated Poisson regression, or a zero-inflated negative binomial regression is most appropriate for analyzing our past 3-month frequency outcome (count variable). To do this, we will run all four models, conducting model fit tests to compare AIC values, BIC values, and raw scores for each regression. If all three indices agree (i.e. select the same “best” model of the four possible), we will interpret the results of that regression. If they do not agree (i.e. select different “best” models from the four possible), we will report the results from each of the selected models.

Regardless of model type, we will enter pre-intervention past 3-month frequency of SI as a covariate, and treatment condition as a predictor, of past 3-month frequency of SI at follow-up in the chosen regression(s). We will consider a *p* value of less than .05 for the treatment condition coefficient (in favor of the Project SAVE SSI) as a significant effect of the Project SAVE treatment on frequency of SI in the past 3-months.

***Testing Hypothesis 3: Do teenagers in the Project SAVE SSI condition endorse lower frequency of NSSI in the past 3 months—relative to teenagers in the active control program?***

We will follow the same procedures for hypothesis 2 but replacing “SI frequency in the past 3 months” with “NSSI frequency in the past 3 months.”

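### The differential-dropout test counts unfinished surveys, not missing outcomes, yet it alone decides whether the not-missing-at-random sensitivity analysis is run

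*Combined protocol and SAP*

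**What the plan says.** All of the following is in the combined protocol and SAP, section Testing for Differential Dropout, unless another section is named.

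- **The test.** The plan says "we will use Z-tests of differential proportions where we compare the proportion of people who drop out before completing the study". It is run twice, once for the post-intervention questions and once for the three-month follow-up.
- **The definition.** For the post-intervention test, "a participant must have made it through all post-intervention survey sections"; for follow-up, "a participant must have made it through all follow-up survey sections". Only the closing logistics block is exempt. Neither rule refers to an outcome item.
- **If p > .05.** "we will assume dropout was not dependent on condition assignment and can proceed with interpreting the effects" of intervention assignment.
- **If p < .05.** The result "for this test is less than .05 we will conclude that dropout was dependent on condition assignment". The main analyses are still reported, with limitations, and "if unequal dropout is present, we will run a sensitivity analysis to determine a range of possible effect sizes for our outcomes of interest".
- **Who receives the imputed value.** The analyst is to "impute the lower residual change value (25th percentile) for all dropouts/missing data", and then do the same with the 75th percentile.

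Two other places bear on this. Under the dependent-variable headings, the three outcomes are single items within the full SITBI-R, with zeros filled in for the two counts when display logic skips the question. Under All Other Variables, the Self Hate Scale is given at post-intervention and follow-up, and the DRS-2 at follow-up. The section Imputing Data works at the level of missing values in the variables of interest and does not refer to survey completion.

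**The concern.** The plan explains why unequal dropout matters: if participants who got worse leave before follow-up, neither the completers' data nor imputation from those data will show it. That argument is about outcomes that were never recorded. A participant who reports NSSI frequency and then stops in a later section has a recorded outcome, so counting that person as a dropout does not match the plan's own reason for testing.

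The mismatch has a consequence because the test is a trigger. The percentile analysis is the only planned analysis that departs from missing at random. If late quitting hides a real imbalance in outcome loss, that analysis is not run, and the report says that dropout did not depend on arm. If late quitting differs by arm while outcome loss does not, the analysis and its caveats appear without cause.

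The wording "for all dropouts/missing data" adds a second uncertainty. Dropout has just been defined by survey completion, so it is unclear whether a non-completer's recorded outcome stays in the percentile analysis or is replaced.

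**Working it through.** **What can be reproduced.** The plan gives 500 randomized participants, 250 per arm at 1:1 (2 × 250 = 500), before type 2 exclusions. It states no dropout rate, no power for the dropout test and no sidedness. The rates below are therefore assumptions, and a two-sided test at .05 is assumed.

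**Model.** Let *m* be the proportion with the outcome missing in an arm, and *q* the proportion of those with the outcome recorded who quit later in the survey. The plan's test then compares

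p = m + (1 − m)q

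between arms instead of *m*. With n = 250 per arm, d = |p₂ − p₁| and p̄ the mean of p₁ and p₂:

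se₀ = √[2p̄(1 − p̄)/n], se₁ = √[(p₁(1 − p₁) + p₂(1 − p₂))/n]

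P(reject) = Φ[(d − 1.96 se₀)/se₁] + Φ[(−d − 1.96 se₀)/se₁]

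**Missed imbalance.** Outcome missing in 20% vs 30%, with the same *q* in both arms. For q = 0: se₀ = √(2 × 0.25 × 0.75/250) = 0.0387, se₁ = √[(0.16 + 0.21)/250] = 0.0385, and (0.10 − 1.96 × 0.0387)/0.0385 = 0.626, so power is 0.73.

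| Late quitting q | Tested proportions | Power |
|---|---|---|
| 0% | 20.0% vs 30.0% | 0.73 |
| 2% | 21.6% vs 31.4% | 0.70 |
| 5% | 24.0% vs 33.5% | 0.65 |
| 10% | 28.0% vs 37.0% | 0.58 |
| 20% | 36.0% vs 44.0% | 0.45 |

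Power falls for two reasons: the gap shrinks (from 10 to 8 points at q = 20%) and the variance grows.

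**False trigger.** Outcome missing in 25% of both arms, with *q* differing by arm.

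| Late quitting | Tested proportions | Chance of p < .05 |
|---|---|---|
| 1% vs 3% | 25.75% vs 27.25% | 6.7% |
| 2% vs 5% | 26.50% vs 28.75% | 8.7% |
| 5% vs 15% | 28.75% vs 36.25% | 43% |

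The nominal rate is 5%.

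**The same in counts (assumed), 250 per arm.**

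- Outcome missing in 40 vs 60: z = 0.08/√(2 × 0.20 × 0.80/250) = 2.24, p = 0.025. Add 25 vs 10 late quitters with the outcome recorded, and non-completion is 65 vs 70: z = 0.50, p = 0.61. The sensitivity analysis is skipped.
- Outcome missing in 50 vs 50: p = 1.00. Add 5 vs 30 late quitters, and non-completion is 55 vs 80: z = 2.52, p = 0.012. The sensitivity analysis is triggered with no imbalance in outcome loss.

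**What the ambiguous wording could cover.** If the outcome is missing in 20% (100 of 500) and a further 2%, 5%, 10% or 15% of all participants quit late with the outcome recorded, then 10, 25, 50 or 75 recorded values belong to non-completers. As a share of all non-completers that is 10/110 = 9%, 25/125 = 20%, 50/150 = 33% or 75/175 = 43%.

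**The case against.** Four arguments on the other side deserve weight.

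*The main results do not depend on this test.* A reader might infer that the H1–H3 estimates are biased by the dropout definition. The documents do not support that. Under Imputing Data, multiple imputation and the supplementary non-imputed analysis are both planned without reference to the Z-test, and both work from missing values. If p < .05 the main analyses are still reported. This argument stands in full.

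*Imputing normally means filling gaps.* A reader might infer that the plan instructs the analyst to overwrite recorded outcomes. It does not say so. The stated purpose is to vary how much dropouts may have changed, which makes sense only where the change is unknown. The missing-values-only reading is natural. What remains is that no sentence says recorded values are kept.

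*The scenario depends on survey order.* Neither questionnaire order nor forced-response settings are given. If the SITBI-R items came last and were mandatory, the two definitions would nearly coincide, and participants who never return are dropouts under either. This stands, and it is why no single size can be given. Conversely, if items can be skipped, a completer may lack the outcome.

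*Redefining dropout leaves the larger weakness.* Even on outcome missingness, the test misses a 20% vs 30% imbalance about 27% of the time (1 − 0.73), and equal missingness by arm does not exclude data missing not at random. This also stands, and it strengthens the fix.

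**Conclusion.** The point holds in limited form. The dropout test measures survey completion, while the bias the plan describes, and the imputation it plans, concern missing outcome values. Since that test alone decides whether the percentile sensitivity analysis is run, the analysis may be skipped or triggered for a reason unrelated to loss of the outcome. The statement that dropout did not depend on arm carries the same weakness. Whether recorded outcomes of non-completers are kept in that analysis is left unstated.

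On the assumed rates, the effect runs from negligible (power 0.73 to 0.70; false trigger 6.7%) to moderate (power 0.45; false trigger 43%). The upper end needs a fifth of those who gave the outcome to quit later, or a threefold difference between arms in late quitting, and nothing in the documents shows that either would occur. A false trigger by itself only adds an analysis and a caveat; the missed trigger is the more consequential error. This is worth correcting because the correction is cheap, not because the confirmatory results are in doubt.

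**What to change.** In Testing for Differential Dropout:

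1. For each hypothesis, define dropout as that outcome being missing at its time point: the post-intervention likelihood item for H1, and the follow-up SI and NSSI counts for H2 and H3, after the display-logic zeros are filled. Run the Z-test on that.
2. State that the 25th- and 75th-percentile values are imputed only where the outcome is missing, and that observed values are always kept, whether or not the survey was finished.
3. Report survey completion by arm as a descriptive figure.
4. Preferably, run the percentile sensitivity analysis whatever the Z-test shows. The dropout definition then no longer matters as a trigger, and the analysis no longer depends on a test of limited power.

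The cost is one extra Z-test (three instead of two), a few sentences, and a little more analysis work if item 4 is adopted. No new data are needed. The plan states that no data had been collected at registration.

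### For the two count outcomes, the dropout sensitivity analysis cannot be run as written in the planned models, and its quartile runs do not bound the treatment effect

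*Combined protocol and SAP*

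**What the plan says.** All references are to the combined protocol and SAP.

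- **Trigger.** Under Testing for Differential Dropout, the sensitivity analysis runs only if the dropout Z-test is significant: "value for this test is less than .05 we will conclude that dropout was dependent on condition assignment".
- **Reason given.** The plan's example of harm is "if more control condition participants experienced a worsening of clinical symptoms and dropped out before completing follow-up measures". It adds that "this worsening of symptoms would not be captured by completers’ data (or by data imputed based on the available completers’ data".
- **Procedure.** The analyst is to "calculate residual change for each of our 3 outcomes", then "identify the 25th and 75th percentile values for residual change in each outcome", then "impute the lower residual change value (25th percentile) for all dropouts/missing data". A second run does the same with the 75th percentile. The results are presented as the lower and upper ends of the effect size, with the comment "This approach explicitly assumes data are not missing at random".
- **Models.** Testing Hypothesis 2 analyses the SI frequency with a Poisson, negative binomial, zero-inflated Poisson or zero-inflated negative binomial regression, chosen by fit. Testing Hypothesis 3 applies the same procedure to NSSI frequency.

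The plan does not say how residual change is calculated, whose data supply the percentiles, how a residual becomes a follow-up count, or which model is fitted afterwards. No arm-specific value is described.

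**The concern.** There are two difficulties.

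The first is mechanical. The only models planned for the two frequencies need outcomes of 0, 1, 2 and so on, and a residual is not that kind of quantity.

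The second is coverage. The plan says completers' data cannot show worsening among dropouts. It then takes its scenario values from residuals, which exist only where follow-up was observed. Those values are the edges of the completers' own middle half. With right-skewed counts, the upper edge lies much closer to the average than the worst completers do. One value goes to all dropouts, so the estimate moves mainly through the difference in dropout rates, and worsening in one arm alone is never represented.

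This is the plan's only analysis that departs from missing at random. A reader told that the two runs are the ends of the range would take a result that survives both as robust to dropout, and that inference would not be justified.

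**Working it through.** The plan states no count mean, dispersion, dropout rate or expected effect, so there is no figure to reproduce. All distributional inputs below are assumptions. Ratios are SAVE divided by control, so values below 1 favour SAVE.

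**1. Can the value enter the model?** Take residual change as follow-up minus the prediction from a linear regression on baseline. The 25th percentile was negative in every setting tried, so the raw residual is outside the range of a count model. One assumed setting (Poisson-lognormal, mean 15, dispersion 2, correlation 0.6, 20% extra zeros, capped at the 95th percentile) gives:
- mean follow-up count 10.4 and residual SD 11.1;
- 25th percentile −6.60, and 75th percentile +4.34;
- prediction plus 25th percentile below zero for 22% of youths.

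**2. How large is the worsening value?** In that setting, 4.34/11.1 = 0.39 SD and 4.34/10.4 = 42% of the mean count. A normal outcome would give 0.67 SD. The worst quarter of residuals averages 15.7, which is 15.7/11.1 = 1.41 SD, or 3.6 times the imputed value. Across capped settings:

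| Assumed inputs | 75th percentile, SD | 75th percentile, % of mean | Predicted count below 0 |
|---|---|---|---|
| Poisson-lognormal, mean 8–15, dispersion 0.5–4, correlation 0.3–0.6, 0–20% extra zeros | 0.24–0.63 | 27–52% | up to 29% |
| Negative binomial k 0.3–0.8 or log-normal SD 1.0–1.6, mean 15, correlation 0.3–0.7, 0–20% extra zeros | 0.09–0.48 | 14–53% | 0–46% |
| Range carried forward (a further repeat with skewed, capped counts) | about 0.2–0.6 | 26–46% | 0–40% |

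In that last repeat the 25th percentile was −0.43 to −0.77 SD, and the worst quarter of completers averaged about +1.4 SD.

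**3. Does it handle the scenario the plan describes?** Assume dropout of 35% in control and 20% in SAVE, control dropouts selected for worsening, and a true ratio of 1.00.
- Completers alone give 1.39–1.80.
- The 75th-percentile run gives 1.19–1.40. At the two ends the bias falls from 0.39 to 0.19 and from 0.80 to 0.40, so about half is removed.
- The true mean excess in control dropouts was 6.0–6.7 episodes, against 1.3–2.6 imputed.

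**4. How wide is the reported range?** Use the same dropout rates, no effect in the observed data, missingness at random, mean 10 and dispersion 1–4.
- One common quartile in both arms: 0.95–0.96 (75th) to 1.11–1.13 (25th).
- Quartiles chosen by arm: 0.77–0.79 to 1.37–1.39.
- Control dropouts at the mean of the worst quarter, with SAVE unshifted: 0.63–0.70.

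With dropout of 25% and 15%, the common range is 0.96–0.98 to 1.07–1.09 and the arm-specific range is 0.82–0.84 to 1.24–1.26. At 250 per arm, the dropout test has power 0.97 for 35% against 20% and 0.80 for 25% against 15%, so the analysis would usually be triggered in these cases.

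**5. Common or arm-specific multipliers?** Now put the 35% dropout in SAVE and 20% in control, with a completer ratio of 0.75. Before any multiplier, dropouts have their own arm's completer mean.
- Both arms' dropouts double: 0.75 × (0.65 + 0.35×2)/(0.80 + 0.20×2) = 0.84.
- Both arms' dropouts triple: 0.75 × (0.65 + 0.35×3)/(0.80 + 0.20×3) = 0.91.
- Only SAVE dropouts double: 0.75 × (0.65 + 0.35×2) = 1.01.

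In simulation the plan's two runs span about 0.69–0.76 to 0.89–0.91 here. Worsening in both arms stays inside or at the edge of that span. Doubling in SAVE alone goes beyond it.

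**The case against.** The strongest reply is that this is a wording gap in a conditional sensitivity analysis that decides no hypothesis. On that view, stating the conversion, rounding and floor would settle it. This answers the mechanical difficulty but not the coverage one: a well-defined quartile run still does not bound the effect or represent one-arm worsening.

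Several stronger readings are tempting, and the documents do not support them.

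- **Worsening is not tested at all.** The 75th-percentile run moves in the right direction and, in the scenario above, removes about half the bias.
- **Doubling or tripling dropouts' counts in both arms puts the true ratio at 0.95–1.02, outside the plan's range.** Applied to each arm's own counts, the ratios are 0.84 and 0.91 (0.87–0.89 and 0.92–0.94 after capping). Doubling falls within the range and tripling is marginal. Values near 1 require the arm difference among dropouts to be removed first, and the plan states no such scenario.
- **The residual is linear, or the result is necessarily on a different scale from the main result.** The text says only residual change. Linear is the natural reading, but it is an inference, and adding the residual back to a prediction would allow a ratio to be reported.

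The sizes also depend on skew. NSSI eligibility requires an episode in the past month. Restricting simulated negative binomial baselines to at least one episode gives a negative share of 9–33% at k 0.3–0.5 and 0–11% at k 0.8. SI is a day count bounded near 90 and may be less skewed.

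**Conclusion.** The point holds in a limited form. For SI and NSSI, the sensitivity analysis lacks a step that would produce a valid outcome for the planned models, and its two runs should not be called the ends of the effect size. That part follows from the text alone.

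The size does not. A worsening shift of about 0.2–0.6 SD (26–46% of the mean count), and negative values for 0–40% of dropouts, rest on assumed right-skewed counts, a linear residual and the 95th-percentile cap. The shift is small to moderate, so worsening is under-tested. The more consequential omission is worsening confined to one arm's dropouts, the case the plan itself names.

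The main analysis is not affected. What is affected is how much reassurance about dropout can be drawn for the primary outcome.

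**What to change.** For Hypotheses 2 and 3, replace the three quartile steps with a tipping-point analysis on the count scale, fixed before data are seen:

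1. Impute missing follow-up counts as non-negative whole numbers. The Imputing Data section names no count model, lower bound or rounding, so this must be specified too.
2. Multiply the imputed counts by fixed factors, for example 0.5, 1, 1.5, 2 and 3, varied separately by arm. Common factors alone barely widen the range.
3. Round, apply the same cap, and refit the count model used for the main result.
4. Report the rate ratio at every combination of factors, and the combination at which the Hypothesis 3 verdict changes.

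For Hypothesis 1, shift the imputed category by −1, 0 and +1 within 0–4, also by arm. Delete the statement that the quartile runs give lower- and upper-end estimates.

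The cost is a few sentences of plan text and some further model runs on data already held. The reported range will be wider and may look less favourable.
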